A Phase 3 Study to Evaluate the Efficacy and Safety of Lumasiran in Children and Adults with Primary Hyperoxaluria Type 1

Study Drug

Lumasiran (ALN-GO1)

Phase

Phase 3

Study Center(s)

The study will be conducted at approximately 20 clinical study centers worldwide.

Objectives and Endpoints

Primary	

To evaluate the effect of lumasiran on percent reduction in urinary oxalate excretion	
Percent change in 24-hour urinary oxalate excretion from baseline to Month 6
Secondary 
To characterize the effect of lumasiran on absolute levels of urinary oxalate excretion, oxalate:creatinine ratios, and plasma oxalateTo evaluate the effect of lumasiran, on renal functionTo evaluate the long-term treatment effect of lumasiran	
Absolute change in 24-hour urinary oxalate corrected for body surface area (BSA) from baseline to Month 6Change in 24-hour urinary oxalate:creatinine ratio (value/upper limit of normal [ULN]) from baseline to Month 6Proportion of patients with 24-hour urinary oxalate level at or below $1.5 \times \text{ULN}$ at Month 6Proportion of patients with 24-hour urinary oxalate level at or below ULN at Month 6Percent change in plasma oxalate from baseline to Month 6Absolute change in plasma oxalate from baseline to Month 6

	
• Change in estimated glomerular filtration rate (eGFR) from baseline to Month 6• Change from baseline (percent and absolute) in 24-hour urinary oxalate excretion, percentage of time that 24-hour urinary oxalate is $\leq 1.5 \times$ ULN, 24-hour urinary oxalate:creatinine ratios and eGFR in the extension periods
Exploratory	
• To evaluate quality of life (QoL)• To evaluate the change in nephrocalcinosis and renal stones• To evaluate the additional pharmacodynamic (PD) parameters of plasma glycolate, urinary glycolate, and urinary oxalate in spot urine collections• To characterize the pharmacokinetics (PK) of lumasiran• To assess for antidrug antibodies (ADA) against lumasiran• To evaluate the effects of lumasiran on patient and caregiver resource use• To describe the patient experiences on lumasiran in PH1 patients and the experiences of caregivers for these patients• Change in Kidney Disease Quality of Life Questionnaire (KDQOL) for patients ≥ 18 years of age at screening, and the Pediatric Quality of Life Inventory (PedsQL [the generic and end-stage renal disease (ESRD) modules]) for patients < 18 years of age at screening• Change in Euro Quality of Life Health State Profile Questionnaire (EQ-5D) and EQ-5D Visual Analog Scale (VAS)• Change in rate of renal stone events• Change in nephrocalcinosis as assessed by renal ultrasound• Change in urinary and plasma glycolate• Change in urinary oxalate:creatinine ratios as assessed in random spot urine collections• PK profile of lumasiran• Frequency of ADA• Change in patient resource use (eg, work/school attendance, visits to doctor/hospital)• Change in patient and caregiver experiences as evaluated by patient and caregiver experience surveys
Safety	
• To evaluate the safety and tolerability of lumasiran• Frequency and seriousness of adverse events (AEs) during the 6-month double-blind treatment period and in the extension periods

Study Design

This is a multicenter, multinational Phase 3 study designed to evaluate the efficacy and safety of lumasiran in patients with PH1 ≥ 6 years of age with relatively preserved renal function. The study will be conducted in 3 parts: a 6-month, placebo-controlled, double-blind treatment period followed by a 3-

month blinded treatment extension period and an open-label extension period of up to 51 months. A schematic of the study design is shown in [Figure 1](#).

Number of Planned Patients

The planned enrollment for this study is 30 patients.

Diagnosis and Main Eligibility Criteria

This study will include adults and children (≥ 6 years of age) with a documented diagnosis of PH1 based on urinary oxalate excretion ≥ 0.70 mmol/24h/1.73m² and confirmed alanine glyoxylate aminotransferase (*AGXT*) mutations, and eGFR ≥ 30 mL/min/1.73m² at screening.

Study Drug, Dose, and Mode of Administration

Lumasiran (ALN-GO1) is an investigational agent comprised of a synthetic, small interfering RNA (siRNA) (drug substance ALN-65585) covalently linked to a triantennary N-acetylgalactosamine (GalNAc) ligand, designed to target liver *hydroxyacid oxidase 1 (HAO1)* mRNA, blocking production of glycolate oxidase (GO) and hence reducing hepatic oxalate production.

Lumasiran will be administered at a dose of 3.0 mg/kg as a subcutaneous (SC) injection. See [Figure 1](#) for the dose schedule.

Reference Treatment, Dose, and Mode of Administration

[figure not shown]
The control drug for this study will be a placebo (sodium chloride 0.9% w/v for SC administration). See [Figure 1](#) for the dose schedule.

Duration of Treatment and Study

The duration of treatment with study drug is up to 5 years, including a 6-month double-blind treatment period followed by a 3-month blinded treatment extension period, and up to a 51-month open-label extension period.

The estimated total time on study, inclusive of screening, for each patient is up to 62 months, including up to 2 months of screening followed by up to 60 months of treatment.

Figure 1: Study Design

Abbreviations: q3M=once every 3 months; qM=once monthly; qMx3=once monthly for 3 consecutive months

* Patients randomized to lumasiran will also receive 2 qM doses of placebo during the 3-month blinded treatment extension period.

Table 1: Schedule of Assessments – 6-Month Double-Blind Treatment Period and Blinded Treatment Extension (Screening through Month 9 Assessments)

Study Visit	Note	Screening	6-Month Double-Blind Treatment Period								3-Month Blinded Treatment Extension Period		
			Base line	Wk 2	M1	M2	M3	M4	M5	M6	M7	M8	M9
Study Day (±Visit Window)		-60 to -1	Day 1	15 (±3)	29 (±4)	57 (±4)	85 (±4)	113 (±4)	141 (±4)	169 (±7)	197 (±4)	225 (±4)	253 (±4)
Informed consent (and assent, if applicable)	If during the study the patient reaches the legal age for consent, the patient needs to consent before any study procedures can be performed	X											
Demographics		X											
Medical history	See Section 6.1.	X	X										
Inclusion/exclusion criteria		X											
Randomization	May be done 1 business day prior to Day 1 for study drug preparation.		X										
Full physical examination	See Section 6.5.3.	X									X		
Symptom-directed physical examination	See Section 6.5.3.		X	X	X	X	X	X	X		X	X	X
Height	In triplicate for pediatric patients. See Section 6.5.2.	X	X								X		
Body weight	See Section 6.5.2.	X	X	X	X	X	X	X	X	X	X	X	X
Vital signs	See Section 6.5.1. On Day 1 and Month 6 only, to be measured predose and 30±10minutes postdose	X	X	X	X	X	X	X	X	X	X	X	X
12-lead electrocardiogram	See Section 6.5.4 and Table 3. For East Asian sites, see Table 4.	X	X					X			X		X

Study Visit	Screening	6-Month Double-Blind Treatment Period									3-Month Blinded Treatment Extension Period		
		Base line	Wk 2	M1	M2	M3	M4	M5	M6	M7	M8	M9	
Study Day (\pm Visit Window)	Note	-60 to -1	Day 1	15 (± 3)	29 (± 4)	57 (± 4)	85 (± 4)	113 (± 4)	141 (± 4)	169 (± 7)	197 (± 4)	225 (± 4)	253 (± 4)
Follicle-stimulating hormone	Only if applicable to confirm postmenopausal status.	X											
Serum pregnancy test (for WOCBP)	See Section 6.5.6.2. Performed after the onset of menarche, if applicable.	X											
Urine pregnancy test (for WOCBP)	May be performed more frequently where required per local requirements, or if pregnancy is suspected. See Section 6.5.6.2.		X		X	X	X			X	X	X	X
DNA sample for PH1/AGXT mutation analysis	Only for patients without documented PH1 genetic analysis.	X											
Exploratory DNA sample (optional)	See Section 6.6.		X										
Clinical laboratory assessments	See Section 6.5.6.	X	X	X	X	X	X	X	X	X	X	X	X
Study drug administration	Dosage is based on total body weight. On M6, all assessments, except PK, should be completed prior to dosing. Quality of life and patient experience and resource-use instruments can be completed after the dose is administered. See Section 5.2.2.		X		X	X	X			X	X	X	X
Blood samples for PK analyses	See Table 3. For East Asian sites, see Table 4.		X				X			X			X
Urine samples for PK analyses	Patients at East Asian sites only; see Table 5.		X							X			

Study Visit		Screening	6-Month Double-Blind Treatment Period								3-Month Blinded Treatment Extension Period		
			Base line	Wk 2	M1	M2	M3	M4	M5	M6	M7	M8	M9
Study Day (±Visit Window)	Note	-60 to -1	Day 1	15 (±3)	29 (±4)	57 (±4)	85 (±4)	113 (±4)	141 (±4)	169 (±7)	197 (±4)	225 (±4)	253 (±4)
Blood sample for PD analyses		X	X		X	X	X	X	X	X	X	X	X
≥3 separate 24-hour urine collection for PD analyses	≥2 collections must be valid. At M6, collect within 14 days prior to dosing. See Section 6.3.1 and Table 7.	X								X			
Single 24-hour urine collection for PD analyses	Collect within 7 days prior to dosing (M1, M2, M3, M7, M8, M9) or visit (M4, M5). If invalid, should be repeated. See Section 6.3.1 and Table 7.				X	X	X	X	X		X	X	X
Random urine sample for PD analysis	See Section 6.3.1 and Section 6.3.1.2 .	X	X	X	X	X	X	X	X	X	X	X	X
Blood sample for pyridoxine (vitamin B6) levels	Only if taking pyridoxine for the treatment of PH1. To be collected ≥6 hours from last dose of pyridoxine. See Section 5.3.	X	X		X	X	X	X	X	X	X	X	X
Renal stone events	See Section 6.3.3.	Continuous											
Renal ultrasound	Analyzed centrally by blinded reader. See Section 6.5.5.	X								X			
Quality of life questionnaires	See Section 6.7.	X								X			
Patient and caregiver experience surveys	See Section 6.8.	X								X			
Patient and caregiver impact questionnaire	See Section 6.9.	X								X			
Healthcare resource utilization	See Section 6.10.	Continuous											

Study Visit		Screening	6-Month Double-Blind Treatment Period								3-Month Blinded Treatment Extension Period		
			Base line	Wk 2	M1	M2	M3	M4	M5	M6	M7	M8	M9
Study Day (\pm Visit Window)	Note	-60 to -1	Day 1	15 (± 3)	29 (± 4)	57 (± 4)	85 (± 4)	113 (± 4)	141 (± 4)	169 (± 7)	197 (± 4)	225 (± 4)	253 (± 4)
Antidrug antibody sample	See Section 6.5.6.1.		X		X		X			X	X		X
Blood and urine samples for exploratory analyses	See Section 6.6.	X	X		X		X			X			X
Review/record adverse events	SAEs (only) are collected in the Screening period. Starting on Day 1, all AEs (ie, including SAEs) are collected. See Section 6.5.7.2.												
Prior and concomitant medications	See Section 5.3.												

Abbreviations: AE=adverse event; AGXT=alanine glyoxylate aminotransferase (gene); DNA=deoxyribonucleic acid; ECG=electrocardiogram; M=month; PD=pharmacodynamic; PH1=primary hyperoxaluria type 1; PK=pharmacokinetic; SAE=serious adverse event; Wk=week; WOCBP=women of child-bearing potential

Notes:

- Assessments to be performed prior to dosing, where applicable. Pregnancy test results must be known prior to dosing, if applicable. Where feasible, when scheduled at the same time points, the assessments of vital signs and 12-lead ECGs should be performed first, before the physical examinations, and blood sample collections.
- Visits and study drug dosing may be conducted offsite where applicable country and local regulations and infrastructure allow (at the discretion of the Investigator, based on safety and tolerability), provided the patient has tolerated a dose of lumasiran administered in the clinic. If a visit is conducted offsite, a body system assessment may be performed in lieu of a physical examination.
- In situations where a study visit is unable to be completed (either at the site or offsite by a healthcare professional), the Investigator (or delegate) will verbally contact the patient within the study visit window to assess concomitant medications, renal stone events, adverse events, and healthcare utilization.
- See Section 4.3.1 for instructions for patients who discontinue study drug.
- Gray-shaded column indicate visits where assessments span 2 days.

Table 2: Schedule of Assessments – Open Label Extension Period (After Month 9 through Year 5)

Study Period	Study Visit	Open-Label Extension Period							Safety Follow-up (Patients who Discontinue Treatment)		
		Through Year 2				Through Year 5					
		M12	M15	M18	M21	M24	M27	M30; M36; M42; M48; M54	EOT M57	EOS/ ET M60	
Study Day (±Visit Window)	Note	337 (±28)	421 (±28)	505 (±28)	589 (±28)	673 (±28)	757 (±28)	Every 168 days (±28)	1597 (±28)	1681 (±28)	Every 84 days (±28)
Informed consent (and assent, if applicable)	If during the study the patient reaches the legal age for consent, the patient needs to consent before any study procedures can be performed										
Full physical examination	See Section 6.5.3.	X		X		X		X		X	
Symptom-directed physical examination	See Section 6.5.3.		X		X						X
Height	In triplicate for pediatric patients. See Section 6.5.2.	X		X		X		X		X	X
Body weight	See Section 6.5.2.	X	X	X	X	X		X		X	X
Vital signs	See Section 6.5.1.	X	X	X	X	X		X		X	X
12-lead electrocardiogram	See Section 6.5.4 and Table 3. For East Asian sites, see Table 4.	X				X		X (M36 and M48 only)		X	
Pregnancy test (WOCBP)	May be performed more frequently where required per local requirements, or if pregnancy is suspected. See Section 6.5.6.2.	X	X	X	X	X	X	X (every 84 days predose)	X	X	X
Clinical laboratory assessments	See Section 6.5.6.	X	X	X	X	X		X		X	X

Study Period	Open-Label Extension Period									Safety Follow-up (Patients who Discontinue Treatment)	
	Through Year 2						Through Year 5				
Study Visit	M12	M15	M18	M21	M24	M27	M30; M36; M42; M48; M54	EOT M57	EOS/ ET M60		
Study Day (±Visit Window)	Note	337 (±28)	421 (±28)	505 (±28)	589 (±28)	673 (±28)	757 (±28)	Every 168 days (±28)	1597 (±28)	1681 (±28)	Every 84 days (±28)
Study drug administration	Study drug to be administered every 3 months through M57. Dosage is based on total body weight. See Section 5.2.2.	X	X	X	X	X	X	X (every 84 [±28] days)	X		
Blood samples for PK analyses	See Table 3. For East Asian sites, see Table 4.	X									
Urine samples for PK analyses	Patients at East Asian sites only; see Table 5.	X									
Blood sample for PD analyses		X	X	X	X	X		X		X	X
≥3 separate 24-hour urine collection for PD analyses	≥2 collections must be valid. Collect within 14 days prior to dosing. See Section 6.3.1 and Table 7 for details.	X									
Single 24-hour urine collection for PD analyses	Collect within 14 days prior to dosing or visit. If invalid, should be repeated. See Section 6.3.1 and Table 7.		X	X	X	X		X		X	X
Random urine sample for PD analysis	See Section 6.3.1 and Section 6.3.1.2.	X	X	X	X	X		X		X	X
Blood sample for pyridoxine (vitamin B6) levels	Only if taking pyridoxine for the treatment of PH1. To be collected ≥6 hours from last dose of pyridoxine. See Section 5.3.	X	X	X							
Renal stone events	See Section 6.3.3.	Continuous									

Study Period	Open-Label Extension Period									Safety Follow-up (Patients who Discontinue Treatment)
	Through Year 2						Through Year 5			
Study Visit	M12	M15	M18	M21	M24	M27	M30; M36; M42; M48; M54	EOT M57	EOS/ET M60	
Study Day (±Visit Window)	337 (±28)	421 (±28)	505 (±28)	589 (±28)	673 (±28)	757 (±28)	Every 168 days (±28)	1597 (±28)	1681 (±28)	Every 84 days (±28)
Renal ultrasound	See Section 6.5.5.	X				X	X (M36 and M48 only)		X	
Quality of life questionnaires	See Section 6.7.	X		X		X	X		X	
Patient and caregiver experience surveys	See Section 6.8.	X		X		X	X		X	
Patient and caregiver impact questionnaire	See Section 6.9.	X		X		X	X		X	
Healthcare resource utilization	See Section 6.10.	Continuous								
Antidrug antibody sample		X		X		X	X		X	X
Blood and urine samples for exploratory analyses	See Section 6.6.	X		X		X	X		X	
Review/record adverse events	See Section 6.5.7.2.	Continuous								
Prior and concomitant medications	See Section 5.3.	Continuous								

Abbreviations: ECG=electrocardiogram; EOS=end of study; EOT=end of treatment; ET=early termination; M=month; PD=pharmacodynamic; PH1=primary hyperoxaluria type 1; PK=pharmacokinetic; WOCBP=women of child-bearing potential.

Notes:

- Assessments are to be performed prior to dosing, where applicable. When applicable, pregnancy test results must be known prior to dosing. When scheduled at the same time points and where feasible, the assessments of vital signs and 12-lead ECGs should be performed before physical examinations, and blood sample collections.
- Visits and study drug dosing may be conducted offsite where applicable country and local regulations and infrastructure allow (at the discretion of the Investigator, based on safety and tolerability), provided the patient has tolerated a dose of lumasiran administered in the clinic. If a visit is conducted offsite, a body system assessment may be performed in lieu of a physical examination.
- Study drug is administered once every 3 months throughout the open-label extension period.

- See Section 4.3.1 for instructions for patients who discontinue study drug.
- In situations where a study visit is unable to be completed (either at the site or offsite by a healthcare professional), the Investigator (or delegate) will verbally contact the patient within the study visit window to assess concomitant medications, renal stone events, adverse events, and healthcare utilization.
- Gray-shaded column indicates the visit where assessments span 2 days.

Table 3: Pharmacokinetic and ECG Assessment Time Points: All Sites except East Asian Sites

Study Month/ Study Day	Sampling Time (hh:mm)	Blood PK Sample	ECG
Screening	Any time during visit		X ^a
Month 0 (Day 1)	Predose	X	X ^b
	04:00 (±1 hour)	X	X ^b
	24:00 (±2 hours)	X	
Month 3 (Day 85± 4 days)	Predose	X	X ^a
	04:00 (±1 hour)	X	
Month 6 (Day 169±7 days)	Predose	X	X ^b
	04:00 (±1 hour)	X	X ^b
	24:00 (±2 hours)	X	
Month 9 (Day 253±4 days)	Predose	X	X ^a
	04:00 (±1 hour)	X	
Month 12 (Day 337±28 days)	Predose	X	X ^a
	04:00 (±1 hour)	X	
	24:00 (±2 hours)	X	
Months 24, 36, 48, 60 (see Table 2)	Predose		X ^a

Abbreviations: ECG=electrocardiogram; hh:mm=hour:minute; PK=pharmacokinetics

Notes:

- Predose samples are collected on the day of dosing.
- The hour (±range) indicate sample collection timing relative to dosing. Precise PK sample times (hour and minute) are recorded. See Section 7.2.7 for additional information on PK assessments.

- Patients should be supine for at least 10 minutes before each ECG is obtained. See Section 6.5.4 for additional information on ECG assessments.
- Blood samples for PK assessment may be collected at 24 hours postdose as feasible during periods of time when the COVID-19 pandemic impedes the ability of patients to travel to the study site and the healthcare professionals to go to the patients' homes.

^a For Screening, Month 3, Month 9, Month 12 and annual visits (Month 24, Month 36, Month 48, Month 60), singlicate ECGs are performed using a local ECG machine. During periods of time when the COVID-19 pandemic impedes the ability of patients to travel to the study site, ECG assessments may be completed up to 7 months after the intended timepoint for visits at Month 12 and later.

^b For Month 0 (Day 1) and Month 6, triplicate ECGs are performed predose and postdose timepoints using a central machine and central reads. Triplicate ECG readings occur approximately 5 minutes apart.

Table 4: Pharmacokinetic and Electrocardiogram Assessment Time Points: East Asian Sites

Study Month (Study Day)	Sampling Time (hh:mm)	Blood PK Sample	ECG
Screening	Any time during visit		X ^a
Month 0 (Day 1)	Predose	X	X ^b
	00:30 (±10 min)	X	
	02:00 (±20 min)	X	
	04:00 (±20 min)	X	X ^b
	06:00 (±20 min)	X	
	08:00 (±20 min)	X	
	24:00 (±2 hours)	X	X ^b
Month 3 (Day 85±4 days)	Predose	X	X ^a
	04:00 (±1 hour)	X	
Month 6 (Day 169±7 days)	Predose	X	X ^b
	00:30 (±10 min)	X	
	02:00 (±20 min)	X	
	04:00 (±20 min)	X	X ^b
	06:00 (±20 min)	X	

Study Month (Study Day)	Sampling Time (hh:mm)	Blood PK Sample	ECG
	08:00 (\pm 20 min)	X	
	24:00 (\pm 2 hours)	X	X ^b
Month 9 (Day 253 \pm 4 days)	Predose	X	X ^a
	04:00 (\pm 1 hour)	X	
Month 12 (Day 337)	Predose	X	X ^b
	00:30 (\pm 10 min)	X	
	02:00 (\pm 20 min)	X	
	04:00 (\pm 1 hour)	X	X ^b
	06:00 (\pm 20 min)	X	
	08:00 (\pm 20 min)	X	
	24:00 (\pm 2 hours)	X	X ^b
Months 24, 36, 48, 60 (see Table 2)	Predose		X ^a

Abbreviations: ECG=electrocardiogram; hh:mm=hour:minute; PK=pharmacokinetics

Notes:

- East Asian includes sites in China, Korea, Japan, Taiwan, and Hong Kong.
- Predose samples are collected on the day of dosing.
- The hour (\pm range) indicate sample collection timing relative to dosing. Precise PK sample times (hour and minute) are recorded. See Section [7.2.7](#) for additional information on PK assessments.
- Patients should be supine for at least 10 minutes before each ECG is obtained. See Section [6.5.4](#) for additional information on ECG assessments.

^a For Screening, Month 3, Month 9, and annual visits (Month 24, Month 36, Month 48, Month 60), singlicate ECGs are performed using a local ECG machine.

^b For Month 0 (Day 1), Month 6, and Month 12 triplicate ECGs are performed predose and postdose timepoints using a central machine and central reads.

Triplicate ECG readings occur approximately 5 minutes apart.

Table 5: Urine Pharmacokinetic Assessment Time Points: East Asian Sites

Study Day	Sampling Time (hh:mm)	Pooled Urine PK Sample
Month 0 (Day 1)	Predose	X
	0-6 hours (± 30 min)	X
	6-12 hours (± 30 min)	X
	12-24 hours (± 2 hours)	X
Month 6 (Day 169 ± 7 days)	Predose	X
	0-6 hours (± 30 min)	X
	6-12 hours (± 30 min)	X
	12-24 hours (± 2 hours)	X
Month 12 (Day 337 ± 7 days)	Predose	X
	0-6 hours (± 30 min)	X
	6-12 hours (± 30 min)	X
	12-24 hours (± 2 hours)	X

Abbreviations: hh:mm=hour:minute; PK=pharmacokinetics

Notes:

- East Asian includes sites in China, Korea, Japan, Taiwan, and Hong Kong.
- The hour (\pm range) indicate sample collection timing relative to dosing. Precise PK sample times (hour and minute) are recorded. See Section 6.4.1 and Section 7.2.7 for additional information on PK assessments.
- All predose samples are spot urine samples; postdose urine samples are pooled samples.

TABLE OF CONTENTS

SPONSOR PROTOCOL APPROVAL	2
INVESTIGATOR'S AGREEMENT	3
PROTOCOL SYNOPSIS	4
TABLE OF CONTENTS.....	18
LIST OF TABLES.....	22
LIST OF FIGURES	22
LIST OF ABBREVIATIONS AND DEFINITIONS OF TERMS.....	23
1. INTRODUCTION	26
1.1. Disease Overview	26
1.2. Lumasiran (ALN-GO1)	27
1.2.1. Summary of Nonclinical Data with Lumasiran	27
1.2.2. Summary of Clinical Data with Lumasiran	28
1.3. Study Design Rationale	28
1.4. Dose Rationale.....	29
1.5. Benefit-Risk Assessment.....	30
2. OBJECTIVES AND ENDPOINTS	31
3. INVESTIGATIONAL PLAN.....	32
3.1. Summary of Study Design.....	32
3.2. Duration of Treatment	34
3.3. Duration of Study	34
3.3.1. Definition of End of Study for an Individual Patient	34
3.4. Number of Planned Patients	34
3.5. Method of Assigning Patients to Treatment Groups	34
3.6. Blinding	34
3.6.1. Emergency Unblinding.....	35
3.7. Data Monitoring Committee.....	36
4. SELECTION AND WITHDRAWAL OF PATIENTS	36
4.1. Inclusion Criteria	36
4.2. Exclusion Criteria	36
4.3. Removal from Therapy or Assessment.....	37

4.3.1.	Discontinuation of Study Drug	38
4.3.2.	Stopping a Patient's Study Participation	38
4.3.3.	Replacement of Study Patients	39
4.3.4.	Lost to Follow-Up.....	39

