3.6. Blinding

All site personnel (with the exception of some site pharmacists) and patients (including their families or caregivers) will be blinded to study drug treatment assignment until the last patient completes the assessments at the Month 9 visit. Site pharmacists may be unblinded to study drug treatment only where required by documented pharmacy procedure. All Sponsor personnel with direct oversight of the conduct and management of the study (except for staff involved in randomization and study drug supply) will be blinded to study drug treatment until the 6-month

treatment period data is unblinded for the primary analysis. Sponsor personnel who may have treatment assignment information will not have access to patient level data from the clinical trial databases.

The independent DMC and an independent biostatistics group will have access to patient level treatment assignments.

To maintain the blind to treatment assignment, during the 3-month blinded treatment extension period, study drug will continue to be administered in a double-blind manner and at the same frequency as in the 6-month double-blind period. However, the study is designed so that all patients will receive active drug during the extension period according to initial treatment assignment as follows:

- Patients randomized to placebo: 3.0 mg/kg lumasiran administered as monthly loading doses (Month 6, 7, and 8)
- Patients randomized to lumasiran: 3.0 mg/kg lumasiran administered as a single maintenance dose at Month 6

Therefore, all site personnel and patients will be aware that all patients will receive active drug administered at Month 6 even though all doses of study drug will be masked.

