6.5.5. Renal Ultrasound

Renal ultrasounds will be obtained as specified in the Schedules of Assessments ([Table 1](#) and [Table 2](#)). Renal ultrasound will be performed according to instructions provided in the Study Manual in a standardized manner. Renal ultrasounds will be reviewed centrally and those obtained at Screening and Month 6 will be read in a blinded manner.

During periods of time when the COVID-19 pandemic impedes the ability of patients to travel to the study site, renal ultrasounds may be completed up to 7 months after the intended timepoint for visits at Month 12 and later.

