6.7. Quality of Life (QOL)

QOL questionnaires will be used to evaluate overall health status and quality of life at the timepoints listed in [Table 1](#) and [Table 2](#). During periods of time when the COVID-19 pandemic impedes the ability of patients to travel to the study site, the KDQOL, PedsQL, and the EQ-5D questionnaires can be completed up to 4 months after the intended time point.

The age of the patient at screening will determine which age-specific questionnaires will be utilized for the duration of the study.

QOL assessments include the following:

- KDQOL, specifically the KDQOL-36 for patients ≥ 18 years of age at screening, and the PedsQL, including the generic and ESRD modules (parent and/or self-report versions) [Salido-Guadarrama 2014] for patients <18 years of age at screening.
- EQ-5D: a standardized instrument consisting of a questionnaire and a visual analog scale pertaining to 5 dimensions. Scoring of the questionnaire is based on degrees of disability. Scoring of the visual analog scale is based on a visual scale ranging from 0 (worst imaginable health state) to 100 (best imaginable health state). Higher scores indicate better health status. The EQ-5D-5L questionnaire will be utilized in patients ≥ 18 years of age at screening, and the EQ-5D-Y questionnaire will be utilized in patients <18 years of age at screening, where available.[Herdman 2011]

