7.1. Determination of Sample Size

The planned enrollment for the study is 30 patients.

Patients will be randomized 2:1 to receive lumasiran or placebo, respectively. Assuming the mean percent reduction from baseline to Month 6 in 24-hour urinary oxalate corrected for body surface area (BSA) is 17% in the placebo arm and the standard deviation in both arms is 25%, 24 patients will provide 90% power to detect a treatment difference of 37% at a 2-sided 5% significance level (ie, 54% reduction in the lumasiran arm). To account for potential drop-outs, 30 patients are planned to be enrolled in the study.

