### 5.8. Visit Windows

For table and figure summaries of the DB period, all data will be tabulated and analyzed per the evaluation visit as recorded on the electronic case report forms (eCRF) even if the assessment is outside of window.

For table and figure summaries of the during lumasiran treatment, the data collected at study visits during the extension period will be re-mapped for the patients randomized to placebo to reflect the visit relative to the first dose of lumasiran (e.g. Month 7 re-mapped to Month 1), Month 8 re-mapped to Month 2, etc.).

Unless otherwise specified, data collected at an unscheduled visit will be included in by patient listings and/or spaghetti plot figures, but no assignment of the scheduled visit will be made for the purposes of summary tabulations. However, unscheduled study visits will be used in the calculation of baseline values and for the any categorical shift tables (e.g. shift from baseline to worst post-baseline value).

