To explore changes in Quality of Life (QoL), patient resource use and patient experience (or caregiver experience) questionnaires will be collected at baseline and every 6 months during the course of the study.

Changes in patient resource use and/or patient experience (or caregiver experience) will be summarized descriptively.

The QoL instrument will be based upon the age of the patient at screening and the instrument will be used consistently throughout the study. Table 3 outlines the QOL instruments to be collected based upon age at screening.

**Table 3:** QOL instruments by Age at Screening (<18 years old vs. ≥ 18 years old)

Age at Screening	QOL Instruments	Domains/Subscales	Notes	
≥18 years old	EQ-5D-5L	5 domains (5 ordinal levels per domain): mobility, self-care, usual activities, pain/discomfort and anxiety/depression  1 scale: Visual Analogue Scale Score  1 summary score: Index Score (representing health state utility for an average individual with the same combination of per-domain responses as the trial participant in question)	VAS is a common variable in both instruments	
<18 years old	EQ-5D-Y	5 domains (3 ordinal levels): mobility, looking after myself, doing usual activities, pain/discomfort and feeling worried/sad/unhappy 1 scale: Visual Analogue Scale Score		
≥18 years old	KDQOL-36	5 subscales: SF-12 Physical Component Summary Score, SF-12 Mental Component Summary Score, Symptoms/Problems, Effects of Kidney Disease and Burden of Kidney Disease	No common variables	
<18 years old	PedsQL	4 domains: Physical Functioning, Emotional Functioning, Social Functioning and School Functioning 3 summary scores (total score, physical health summary score and psychosocial health summary score)	- variables	
<18 years old	PedsQL ESRD	7 domains: General Fatigue, About My Kidney Disease, Treatment Problems, Family and Peer Interaction, Worry, Perceived Physical Appearance, and Communication 1 summary score: Total Score		

As shown in Table 3, the EQ-5D will be collected to measure general health status in both pediatrics and adult patients with PH1. The VAS and Index Score will range from 0 to 100 where lower values represent a worse quality of life.

During the double-blind period, the change from baseline to month 6 in VAS (pooling: EQ-5D-5L and EQ-5D-Y) will be summarized by randomized treatment arm (lumasiran or placebo),

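### Month 6 questionnaires may be completed after the known-active Month 6 dose, or up to 4 months late under the COVID-19 allowance, and the SAP conflicts on whether such forms enter the placebo comparison

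*Protocol*

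**What the plan says.** **Schedule.** From Screening to Month 9, Protocol Table 1 schedules the quality-of-life questionnaires, experience surveys and impact questionnaire at Screening and Month 6 only.

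**Order at Month 6.** The study drug row of Table 1 first asks for every Month 6 assessment except PK before dosing, then makes an exception: "Quality of life and patient experience and resource-use instruments can be completed after the dose is administered". Protocol 5.2.2 places the Month 6 dose after completion of all assessments and makes no exception.

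**Knowledge of treatment.** Protocol 3.6 states that "all site personnel and patients will be aware that all patients will receive active drug administered at Month 6".

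**COVID-19 allowance.** Protocol 6.7 says that, while the pandemic impedes travel to the site, "the KDQOL, PedsQL, and the EQ-5D questionnaires can be completed up to 4 months after the intended time point". Sections 6.8 and 6.9 say the same for the experience surveys and the impact questionnaire. None of the three names a visit to which the allowance is limited. Section 6.5.5 does: "renal ultrasounds may be completed up to 7 months after the intended timepoint for visits at Month 12 and later". Section 6.5.4 has the same limit for ECGs.

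**Analysis.** SAP 5.8 tabulates double-blind data by visit "as recorded on the electronic case report forms (eCRF) even if the assessment is outside of window". SAP 5.2 includes in the efficacy summaries everything up to and including the Month 6 visit, but also defines the double-blind period as ending at the date and time of the first extension dose. SAP 7.4 summarizes "the change from baseline to month 6 in VAS" by randomized arm and describes the other instruments.

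**The concern.** Placebo patients cross over to lumasiran at Month 6. A questionnaire that stands for the placebo experience has to be completed before that dose. The protocol allows later completion by two routes, and they differ in weight.

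- **Same-day completion after the dose (Table 1 note).** The patient has had hours of exposure and knows the dose was active. Any effect is one of expectation, and it is open to both arms.
- **Late completion under the COVID-19 allowance (Sections 6.7 to 6.9).** A placebo patient could by then have been through the whole loading phase. The form would describe life on lumasiran but carry the label placebo, Month 6.

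At stake is the only randomized comparison of these instruments. It cannot be collected again after crossover. The SAP does not settle what happens to such a form, because one of its rules keeps it and another drops it.

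**Working it through.** **1. The plan's own figure.** The only sample-size statement concerns urinary oxalate, not the questionnaires. Protocol 7.1 says "24 patients will provide 90% power to detect a treatment difference of 37% at a 2-sided 5% significance level" and that "the standard deviation in both arms is 25" percent. At 2:1, 24 patients are 16 and 8. For a two-sample t-test the noncentrality is 37 / (25 × √(1/16 + 1/8)) = 37 / 10.83 = 3.42 on 22 degrees of freedom, which gives power of 90.4%. The stated 90% is reproduced. Nothing below alters it. The 30 patients to be enrolled split into about 20 lumasiran and 10 placebo.

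**2. How late a form can be, and after how many doses.** Table 1 puts Month 6 at Day 169 and Months 7, 8 and 9 at Days 197, 225 and 253.

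- With 28-day months: 169 + 4 × 28 = Day 281.
- With calendar months: 169 + 4 × 30.4 = about Day 291.
- Time since a placebo patient's first lumasiran dose: 112 to 122 days.
- Time since the Month 9 dose: 281 − 253 = 28 days, to 291 − 253 = 38 days.

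Under Protocol 3.1 a placebo patient on schedule has received lumasiran at Months 6, 7, 8 and 9 by then. That is four doses, as many as the lumasiran arm received in the double-blind period (Day 1, Months 1, 2 and 3).

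**3. What the SAP does with such a form.**

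- SAP 5.8 (visit label, even if out of window): kept as placebo, Month 6.
- SAP 5.2, efficacy summaries (all data through the Month 6 visit): kept.
- SAP 5.2, definition of the double-blind period (before the first extension dose): excluded.
- SAP 5.2, during-lumasiran summaries (assessments from the first lumasiran dose on): the same form qualifies by date.
- SAP 5.4, crossover baseline (last value before the first lumasiran dose): the form cannot serve, so baseline falls back to Screening, more than five months before Month 6.

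**4. Dilution if the form is kept.** Let Δ be the true difference, k the number of late placebo forms out of about 10, and g the share of the full effect that each shows. The placebo mean moves by (k/10) × g × Δ, so the share of Δ that remains is 1 − (k/10) × g. This assumes that lateness does not change the lumasiran arm's mean.

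| k of 10 | g = 0.25 | g = 0.5 | g = 1 |
|---|---|---|---|
| 1 | 97.5% | 95% | 90% |
| 3 | 92.5% | 85% | 70% |
| 5 | 87.5% | 75% | 50% |

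Neither k nor g is in the documents. The table shows a range and does not forecast what happened.

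**The case against.** **The late route is narrow.** It applies only while the pandemic impedes travel, and it does harm only if the Month 6 dose is given while the questionnaire waits. If the whole visit slips, the form still precedes lumasiran. Month 6 also carries post-dose vital signs and triplicate ECGs on a central machine, and dosing at home by a professional starts at Month 12. A patient dosed at the site has little reason to use a travel allowance. This stands as a limit on likelihood. It does not close the route, because the COVID-19 provision in Protocol 5.2.2 for dosing by the patient or caregiver has no visit limit either.

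**It may never have applied.** The investigator letter is dated 02 April 2020 and Amendment 3 is dated 06 May 2020. Amendment 3 widened visit windows only in the open-label schedule. The documents do not say whether any Month 6 visit was still to come. This stands: a reader might infer that Month 6 data were in fact contaminated, and nothing in the documents shows it.

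**The SAP predates the allowance.** It is based on Amendment 2, and Protocol 7.2 promises COVID-19 summaries in the SAP. That explains the gap, but the SAP provided contains no such rule. The listings do carry a period variable, so late forms can be traced and need not be lost.

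**Same-day completion is minor.** Both arms receive an active dose at Month 6 and know it. A reader might infer a bias toward zero from the Table 1 note alone, but the documents give no basis for one. A form completed just before the dose is also filled in by someone who knows that active drug comes next.

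**The stakes are limited.** The instruments are exploratory, described rather than tested, and outside the hierarchy in SAP 5.6. This stands in full.

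**Conclusion.** The concern holds as a defect in the rules for exploratory data. The 4-month allowance as written reaches Month 6. Two SAP rules would then place a post-crossover form in the placebo column, and a third would remove it. The direction is probably dilution. With 3 of about 10 placebo patients late, 70% to 92.5% of the difference remains if each shows 100% to 25% of the full effect. Those counts and shares are assumptions, and 70% is the unfavourable end.

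Two broader readings are not supported. A reader might take the questionnaires to be the only placebo-controlled patient-reported data. Protocol 6.10 describes healthcare resource utilization as patient-reported, and Table 1 collects it continuously, so the accurate statement is that Month 6 is the only post-baseline placebo-controlled time point for these questionnaires and surveys. A reader might also suspect the main efficacy result. The primary and secondary endpoints, power and alpha are unaffected.

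**What to change.** 1. In Protocol 6.7 to 6.9, limit the 4-month allowance to visits at Month 12 and later, as 6.5.4 and 6.5.5 already do.
2. Record the completion date and time of each Month 6 instrument relative to the Month 6 dose. State in SAP 5.2, 5.8 and 7.4 that instruments completed after the first extension dose are excluded from the double-blind comparison, or shown separately, with a count by arm.
3. Reconcile the Table 1 note with Protocol 5.2.2, preferably by having the instruments completed before the Month 6 dose.

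The cost is three short edits to the allowance, one table note, a completion date/time field if the eCRF lacks one, and a sentence or two in the SAP. The downside is possibly a few missing Month 6 forms, each about 10% of a placebo arm of 10. The first two changes deal with the route that matters. The third removes a contradiction in the text and has little effect on bias.
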